#### 7.2.7.1.3 Missing items

The method used for both health-related quality of life (HRQL) instruments requires that for multi-item scales, at least half of the items from the scale have been answered. The missing items are imputed based on the average of those items that are answered. None of the single item measures can be imputed using this method of imputation. In the event of missing full assessments, none of the subscales will be scored or imputed. Tables 1 and 2 detail the number of required items for the QLQ-C30 subscales and QLQ-EN24 subscales respectively.

#### 7.2.7.2 Mixed Model Analysis

##### 7.2.7.2.1 Hypothesis

The hypothesis for the HRQL endpoint – change over time in the QLQ-C30 GHS/QOL is as follows:

- H0: There is no difference in health-related quality of life based on the EORTC QLQ C-30 GHS/QOL scale between AEZS-108 and doxorubicin treated subjects.
- Ha: Treatment with AEZS-108 is associated with better health-related quality of life based on the EORTC QLQ C-30 GHS/QOL scale as compared to treatment with doxorubicin.

The same set of hypotheses holds for QLQ-EN24.

HRQL assessments are performed at the following visits:

Screening, end of cycles 3 and 6, end of therapy (3-5 weeks after last dose) and at post therapy follow-up (every 3 months).

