## 4 GENERAL CONVENTIONS

Unless otherwise stated, all analyses will be performed using SAS Version 9.2 or higher and all hypothesis tests will be conducted at a two-sided significance level of 0.05. P-values will be presented with 3 decimals and p-values that are less than 0.001 will be presented as < 0.001.

Continuous (non-survival related) data will be summarized using descriptive statistics: number of observations (n), mean, standard deviation (SD), median, minimum, and maximum. Frequencies and percentages will be used to summarize categorical (discrete) data. Presentations of categorical data will generally suppress percentages for items where the count is zero in order to draw attention to the nonzero counts. In general, mean, standard deviation, median, 25th and 75th percentiles, minimum, maximum, and percentages will be presented with one decimal.

Unless otherwise stated, confidence intervals, when presented, will be constructed at the two-sided 95 % level. For binomial variables, the 95 % confidence intervals will be constructed using the normal approximation without continuity correction.

In the tables the following indication for treatment will be used: AEZS-108 and Doxorubicin. Data listings will show data presented in the summary tables by study drug, country, center and patient number.

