**Table 2: QLQ-EN24 scales and scoring details**

	Number of Items	Item Range a	Item Numbers	Minimum Not Missing
Functional Scales				
Sexual Interest	1	3	49	N/A
Sexual Activity	1	3	50	N/A
Sexual Enjoyment	1	3	54	N/A
Symptom Scales / Items				
Lymphoedema	2	3	31-32	1
Urological symptoms	4	3	34-37	2

	Number of Items	Item Range a	Item Numbers	Minimum Not Missing
Gastrointestinal symptoms	5	3	38-42	3
Poor body image	2	3	47-48	1
Sexual/vaginal problems	3	3	51-53	2
Pain in back and pelvis	1	3	33	N/A
Tingling/numbness	1	3	43	N/A
Muscular pain	1	3	44	N/A
Hair loss	1	3	45	N/A
Taste change	1	3	46	N/A

a Range is the difference between the maximum possible value of the raw score and the minimum possible value.

A high score for the functional scales represents a high level of functioning, while a high score for the symptom scales represents a high level of symptoms or problems. Symptoms related to sexual/vaginal problems (including items 51-53) are optional.

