#### 7.2.7.2.3 Description of mixed model with assumptions

Changes over time in QLQ-C30 Global Health Status/QOL scores and in QLQ-EN24 scores will be compared between treatment groups using a restricted maximum likelihood-based mixed model for repeated measures (MMRM) data under the missing at random (MAR) assumption (Mallinckrodt et al, 2008).

The dependent variable of this model will be the change of QLQ-C30 Global Health Status/QOL score or the QLQ-EN24 score measured at the end of cycles 3 and 6, at the end of therapy and at post therapy follow-up as compared to baseline (denoted by HRQL). The model will include the fixed, categorical effects of treatment (trt), visit (visit), and treatment-by-visit interaction (trt\*visit). As there is only a limited amount of time points per subject and given the possibility that not all time points are equally spaced in time, time is entered into the model as the categorical variable visit. The random subject effects

are not explicitly formulated in the model form, but will be modelled as part of the within-subject error correlation structure. For this purpose, an unstructured covariance matrix will be used, allowing for different variances / covariances across subjects. If the analysis using the unstructured covariance matrix fails to converge, the following covariance structures will be tested: heterogeneous Toeplitz, heterogeneous compound symmetry, Toeplitz and compound symmetry. The covariance structure converging to the best fit, as determined by Akaike's information criterion, will be used as the primary analysis. The Kenward-Roger approximation will be used to estimate denominator degrees of freedom. The least square means for each treatment group and the treatment difference will be presented together with the 95% confidence interval and p-value.

The pseudo SAS code of the primary model is as follows:

```
proc mixed data = HRQLdataset method = reml;
  class PatID trt visit;
  model HRQL = trt visit trt*visit baseline baseline*visit / noint ddfm = kr;
  repeated r / subject = PatID type=un;
run;
```

where PatID represents the individual subject id.

The mixed model will provide estimates of the treatment effect and of the treatment difference at each visit until end of treatment, together with their 95% confidence intervals.

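### The SAP extends a formal quality-of-life hypothesis to the 13 QLQ-EN24 scales without naming the deciding contrast or limiting the error rate across scales and visits

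*SAP*

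**What the plan says.** SAP 7.2.7.2.1 introduces one quality-of-life endpoint, "change over time in the QLQ-C30 GHS/QOL is as follows", and gives it a null hypothesis of no difference and an alternative that AEZS-108 is better. The next sentence reads "The same set of hypotheses holds for QLQ-EN24". Neither statement names a visit, and the second names no scale.

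The table headed "QLQ-EN24 scales and scoring details" (SAP Table 2) lists 3 functional and 10 symptom scales and defines no total score. Its note adds "Symptoms related to sexual/vaginal problems (including items 51-53) are optional".

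SAP 7.2.7.2.3 makes two separate promises from the mixed model. The first is "The least square means for each treatment group and the treatment difference will be presented together with the 95% confidence interval and p-value", without saying whether this difference belongs to one visit or is an average over visits. The second is that the model will give the estimate "of the treatment difference at each visit until end of treatment, together with their 95% confidence intervals". The pseudo-code contains treatment, visit and their interaction, but no statement that picks out a contrast.

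SAP 4 says that, unless stated otherwise, "all hypothesis tests will be conducted at a two-sided significance level of 0.05". SAP 7.2.7 states nothing else. SAP 7.4 orders OS, PFS and ORR in a hierarchy and does not mention quality of life. SAP 9 declares formal safety comparisons post hoc; quality of life carries no such label.

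**The concern.** Quality of life is a stated secondary objective of an open-label trial, and the SAP gives it a formal alternative hypothesis in favour of the new drug. If that hypothesis applies to 14 scales, each at 0.05, and the plan does not say which result decides it, a single favourable scale or visit can be reported as a prespecified positive finding. The reader of the study report could not attach an error rate to such a claim, because the plan does not fix how many looks there were or which one counted.

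**Working it through.** The plan states no error rate for quality of life, so there is no figure of its own to reproduce.

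**Inputs from the documents**
- Scales carrying a hypothesis: 1 (GHS/QOL, SAP 7.2.7.2.1) + 13 (EN24, SAP Table 2) = 14.
- Visits with a between-arm estimate: end of Cycle 3, end of Cycle 6 and end of therapy (SAP 7.2.7.2.1 and 7.2.7.2.3) = 3.
- Level per test: two-sided 0.05 (SAP 4), hence 0.025 in the direction favouring AEZS-108.

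**Assumed, because the documents give no values**
- Correlation of the test statistics: 0 to 0.5 between scales and 0.3 to 0.7 between visits, with 0.7 between scales as a stress case.
- No true difference on any scale at any visit.

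**Independent tests as a reference point**
- 14 tests: 1 − 0.95^14 = 0.512; favouring AEZS-108 only, 1 − 0.975^14 = 0.298.
- 14 × 3 = 42 tests: 1 − 0.95^42 = 0.884; favouring AEZS-108 only, 1 − 0.975^42 = 0.655.

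**With correlation**

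100,000 simulated sets of normal test statistics were drawn. The correlation between two statistics was the between-scale value times the between-visit value. A set counted if any |z| exceeded 1.96, or any z exceeded 1.96 for the one-direction column.

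One contrast per scale (14 tests):

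| Between-scale correlation | Either direction | Favouring AEZS-108 |
|---|---|---|
| 0 | 51% | 30% |
| 0.2 | 47% | 25% |
| 0.3 | 44% | 22% |
| 0.5 | 35% | 17.5% |

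Three by-visit contrasts per scale (42 tests); each range runs from between-visit correlation 0.7 (low end) to 0.3 (high end):

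| Between-scale correlation | Either direction | Favouring AEZS-108 |
|---|---|---|
| 0 | 80–87% | 55–63% |
| 0.3 | 73–81% | 40–49% |
| 0.5 | 62–70% | 32–40% |
| 0.7 (stress case) | 47–56% | 24–30% |

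GHS/QOL alone over three visits gives 11% (between-visit correlation 0.7) to 14% (0.3).

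**Sensitivity to the count**
- Items 51–54 are answered only by sexually active patients (Protocol Appendix 6), so the sexual/vaginal and sexual enjoyment scales apply to a subset. Without them there are 12 scales: 32–46% with one contrast each, and 1 − 0.95^36 = 0.842 for 36 independent tests.
- Table 14.2.20.1 refers to C30 scores in the plural. If all 15 C30 scales in SAP Table 1 are modelled, there are 15 + 13 = 28 scales. One contrast each then gives 49–76%.

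**The case against.** The SAP attaches its p-value to one unspecified treatment difference and promises only confidence intervals at each visit. SAP 7.2.7 and Protocol 9.5.3 likewise promise estimates with intervals. A reader might infer that the plan specifies 42 p-values, but the text does not say so. One overall difference per scale is an equally natural reading of the p-value sentence. This part of the objection stands, and it is why the result is given under both readings. It does not close the gap: a 95% interval that excludes zero is equivalent to a test at 0.05, and the choice between the readings is left open.

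GHS/QOL is also presented as the quality-of-life endpoint, and an EN24 result cannot reject the GHS/QOL null hypothesis. For that hypothesis alone the error is 5% if the overall difference is the test, and 11–14% if any of three visits counts. This stands too, so it would be wrong to say that the GHS/QOL hypothesis has no usable error rate at all. What remains is that no contrast is named even for GHS/QOL, and that EN24 is given hypotheses of the same standing without a single score to test.

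Finally, SAP 7.4 reserves potential labelling claims for PFS and ORR after OS. Quality of life lies outside that hierarchy and cannot disturb it. That stands and limits the consequence to how the quality-of-life results are interpreted.

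**Conclusion.** The gap is real and confined to the quality-of-life objective. The plan applies a formal hypothesis to 14 scales, leaves the deciding contrast open, and neither adjusts for the number of tests nor labels them descriptive. Under the global null and the assumed correlations, the chance of at least one nominally significant difference in either direction is about 35–51% with one contrast per scale. It is 62–87% if the three by-visit intervals are also read as tests. For a false result favouring AEZS-108 the ranges are about 17–30% and 32–63%.

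A reader might infer that a false quality-of-life finding is more likely than not. The documents do not support that without conditions. It needs the by-visit reading and between-scale correlation that is not very high, since at 0.7 the figure is 47–56%. With one contrast per scale it holds only if the scales are nearly independent. For a false finding in favour of AEZS-108, the range under the by-visit reading lies on both sides of one half. Nor is the trial's error control for OS, PFS or ORR affected.

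**What to change.** In SAP 7.2.7.2.1, before database lock, name one GHS/QOL contrast from the planned mixed model as the only test of the quality-of-life hypothesis. One option is the overall treatment difference averaged over end of Cycle 3, end of Cycle 6 and end of therapy. Another is a single visit that the sponsor justifies. The documents do not favour any particular visit. A single early one would narrow the stated objective, which runs to one year after treatment. Because post-therapy follow-up also enters the model, write the contrast out explicitly, so that it is clear which visits it averages.

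Delete "The same set of hypotheses holds for QLQ-EN24". Report by-visit GHS/QOL differences, all EN24 scales and any other C30 scales as descriptive estimates with 95% confidence intervals and no p-values.

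The cost is a few SAP sentences and fewer p-values in Tables 14.2.20.1 and 14.2.20.2, with no new data, visits or models. The downside is that nominal significance on single scales or visits can no longer be claimed.

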#### 7.2.7.2.2 Missingness

Missingness can be classified in terms of missing items (i.e. specific item(s) not completed on an otherwise completed form) or missing forms (i.e. entire form not completed). Furthermore, missing forms can be classified in terms of intermittent missing (i.e. missing assessment(s) between two non-missing assessments) or monotone missing (i.e. missing all assessments after a certain time point possibly due to subject dropout or treatment discontinuation).

In this study, as the HRQL data capture is scheduled up to the end of therapy and post therapy visits and subjects are expected to experience certain disease- or treatment-related morbidity that will lead to discontinuation of study treatment, missing assessments are inevitable. Also missing full assessments even for the subjects still on treatment can occur despite the best effort to minimize those. The underlying reasons for missing data are unknown but, in general, 3 different missing data mechanisms are considered (Rubin 1976; Little and Rubin, 1987; Fairclough, 2002).

- **Missing Completely at Random (MCAR)**  
Missingness is assumed to be completely unrelated to the HRQL scores. In general, this assumption is not plausible in oncology studies and will therefore not be assumed for the analyses.
- **Missing at Random (MAR)**  
Missingness depends only on observed data (e.g. prior observed HRQL scores or observed covariates). This is the assumption underlying the mixed modelling approach described here.
- **Missing Not at Random (MNAR)**  
Missingness depends on the HRQL scores that are missing. Since we have not observed the missing HRQL scores, it is not possible to test if the missingness of HRQL data depends on the value they would have had if not missing. However, the possibility of missing not at random may not be completely ruled out.

#### 7.2.7.2.3 Description of mixed model with assumptions

Changes over time in QLQ-C30 Global Health Status/QOL scores and in QLQ-EN24 scores will be compared between treatment groups using a restricted maximum likelihood-based mixed model for repeated measures (MMRM) data under the missing at random (MAR) assumption (Mallinckrodt et al, 2008).

The dependent variable of this model will be the change of QLQ-C30 Global Health Status/QOL score or the QLQ-EN24 score measured at the end of cycles 3 and 6, at the end of therapy and at post therapy follow-up as compared to baseline (denoted by HRQL). The model will include the fixed, categorical effects of treatment (trt), visit (visit), and treatment-by-visit interaction (trt\*visit). As there is only a limited amount of time points per subject and given the possibility that not all time points are equally spaced in time, time is entered into the model as the categorical variable visit. The random subject effects

are not explicitly formulated in the model form, but will be modelled as part of the within-subject error correlation structure. For this purpose, an unstructured covariance matrix will be used, allowing for different variances / covariances across subjects. If the analysis using the unstructured covariance matrix fails to converge, the following covariance structures will be tested: heterogeneous Toeplitz, heterogeneous compound symmetry, Toeplitz and compound symmetry. The covariance structure converging to the best fit, as determined by Akaike's information criterion, will be used as the primary analysis. The Kenward-Roger approximation will be used to estimate denominator degrees of freedom. The least square means for each treatment group and the treatment difference will be presented together with the 95% confidence interval and p-value.

The pseudo SAS code of the primary model is as follows:

```
proc mixed data = HRQLdataset method = reml;
  class PatID trt visit;
  model HRQL = trt visit trt*visit baseline baseline*visit / noint ddfm = kr;
  repeated r / subject = PatID type=un;
run;
```

where PatID represents the individual subject id.

The mixed model will provide estimates of the treatment effect and of the treatment difference at each visit until end of treatment, together with their 95% confidence intervals.

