40. Have you been troubled by passing wind?	1	2	3	4
41. Have you had cramps in your abdomen?	1	2	3	4
42. Have you had a bloated feeling in your abdomen?	1	2	3	4
43. Have you had tingling or numbness in your hands or feet?	1	2	3	4
44. Have you had aches or pains in your muscles or joints?	1	2	3	4
45. Have you lost hair?	1	2	3	4
46. Has food and drink tasted differently from usual?	1	2	3	4

Please go on to the next page

ENGLISH

During the past week:		Not at all	A little	Quite a bit	Very much
47.	Have you felt physically less attractive as a result of your disease or treatment?	1	2	3	4
48.	Have you felt less feminine as a result of your disease or treatment?	1	2	3	4
 During the past 4 weeks:					
		Not at all	A little	Quite a bit	Very much
49.	To what extent were you interested in sex?	1	2	3	4
50.	To what extent were you sexually active?	1	2	3	4
Answer these questions only if you have been sexually active during the past 4 weeks:					
51.	Has your vagina felt dry during sexual activity?	1	2	3	4
52.	Has your vagina felt short and / or tight?	1	2	3	4
53.	Have you had pain during sexual intercourse or other sexual activity?	1	2	3	4
54.	Was sexual activity enjoyable for you?	1	2	3	4

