Table 14.2.17.1	Progression-free survival: sensitivity analysis 4: part 1 (Cox models for treatment and each covariate separately)
Table 14.2.17.2	Progression-free survival: sensitivity analysis 4: part 2 (multivariate Cox model)
Table 14.2.18.1	Quality of Life: C30 scores raw data summaries
Table 14.2.18.2	Quality of Life: EN24 scores raw data summaries
Table 14.2.18.3	Quality of Life: individual questions C30 raw data summaries

Table 14.2.18.4	Quality of Life: individual questions EN 24 raw data summaries
Table 14.2.19.1	Quality of Life: C30 scores change from baseline summaries
Table 14.2.19.2	Quality of Life: EN24 scores change from baseline summaries
Table 14.2.19.3	Quality of Life: individual questions C30 change from baseline summaries
Table 14.2.19.4	Quality of Life: individual questions EN 24 change from baseline summaries
Table 14.2.20.1	Quality of Life: mixed model analysis on C30 scores change from baseline
Table 14.2.20.2	Quality of Life: mixed model analysis on EN24 scores change from baseline
Table 14.3.1.1	Summary of occurrence of treatment emergent adverse events (TEAE)
Table 14.3.1.2	Treatment emergent adverse events (TEAE) – by SOC and PT
Table 14.3.1.3	Treatment emergent adverse events (TEAE) (showing PT $\geq$ 5%) – by PT
Table 14.3.1.4	Treatment emergent adverse events (TEAE) – by SOC, PT and severity
Table 14.3.1.5	Related treatment emergent adverse events (TEAE) – by SOC and PT
Table 14.3.1.6	Related treatment emergent adverse events (TEAE) (showing PT $\geq$ 5%) – by PT
Table 14.3.1.7	Summary of TEAEs by relationship to each study treatment –by SOC and PT
Table 14.3.1.8	Summary of TEAEs by combined relationship to each study treatment – by SOC and PT
Table 14.3.1.9	Serious treatment emergent adverse events (TEAE) – by SOC and PT
Table 14.3.1.10	Serious treatment emergent adverse events (TEAE) (showing PT $\geq$ 2%) – by PT
Table 14.3.1.11	Serious treatment emergent adverse events (TEAE) – by SOC, PT and severity
Table 14.3.1.12	Related serious treatment emergent adverse events (TEAE) – by SOC

	and PT
Table 14.3.1.13	Related serious treatment emergent adverse events (TEAE) (showing PT $\geq$ 1.8%) – by PT
Table 14.3.1.14	Grade 3 or 4 serious treatment emergent adverse events (TEAE) – by SOC and PT
Table 14.3.1.15	Grade 5 serious treatment emergent adverse events (TEAE) – by SOC and PT
Table 14.3.1.16	Grade 3 or higher treatment emergent adverse events (TEAE) – by SOC and PT

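### Two EN24 scales (items 51-53 and item 54) apply only to sexually active women, but the SAP puts them through the missing-at-random mixed model and reports a between-arm p-value

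*SAP*

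**What the plan says.** - **Model.** SAP 7.2.7.2.3: "Changes over time in QLQ-C30 Global Health Status/QOL scores and in QLQ-EN24 scores will be compared between treatment groups", by a "mixed model for repeated measures (MMRM) data under the missing at random (MAR) assumption". The outcome is change from baseline at the end of cycles 3 and 6, at end of therapy and at follow-up. The terms are treatment, visit, baseline score, and the interactions of visit with treatment and with baseline. Least square means, a treatment difference, a 95% confidence interval and a p-value are to be shown.
- **Hypotheses and output.** SAP 7.2.7.2.1 extends the superiority hypotheses for the C30 global scale to EN24. Table 14.2.20.2 in Appendix E, "Quality of Life: mixed model analysis on EN24 scores change from baseline", names no exclusion.
- **Questionnaire.** In Protocol Appendix 6, items 51 to 54 of the EN24 stand under the line "Answer these questions only if you have been sexually active during the past 4 weeks". Item 54 is "Was sexual activity enjoyable for you".
- **Scoring.** SAP Table 2 scores items 51-53 as Sexual/vaginal problems (at least two answers needed) and item 54 alone as Sexual Enjoyment. Its note reads "Symptoms related to sexual/vaginal problems (including items 51-53) are optional". It gives no analysis rule and does not mention item 54.
- **Missing data.** SAP 7.2.7.1.3 has a half-scale rule for multi-item scales; for the rest, "None of the single item measures can be imputed using this method of imputation". SAP 7.2.7.2.2 sorts missing data into blank items and blank forms. Neither section has a not-applicable class. Section 7.2.7.2.2 concedes that missingness not at random cannot be excluded, but no sensitivity analysis for it is planned.

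**The concern.** For a woman who was not sexually active, leaving items 51-54 blank is the correct response. No unobserved value lies behind the blank. A missing-at-random model treats that blank as a value that exists and can be projected from what was observed.

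Who answers after baseline is also an outcome of the trial. Illness or toxicity may stop sexual activity, and may do so to a different extent in the two arms. The women compared at a later visit would then differ between arms for reasons that randomisation does not balance. A confidence interval and p-value on such a comparison would be read as a randomised treatment effect on a patient-reported secondary endpoint.

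**Working it through.** The plan states no sample size, effect, standard deviation or completion rate for quality of life, so there is no figure to reproduce. The check is of structure, followed by two illustrations under stated assumptions.

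**1. Extent.** Items per scale in SAP Table 2: 1+1+1+2+4+5+2+3+1+1+1+1+1 = 24 items in 13 scales. The skip instruction covers 3 + 1 = 4 items, which form 2 scales. The other 11 scales, including Sexual Interest (item 49) and Sexual Activity (item 50), carry no skip instruction.

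**2. Who contributes.** SAP 4.1 takes the screening visit as baseline for questionnaires. A change score at a visit needs an answer at both times, so two conditions apply:
- active in the 4 weeks before screening: fixed before randomisation, so it narrows the population but leaves the comparison intact;
- active in the 4 weeks before the visit: after randomisation, and open to influence by treatment or symptoms.

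**3. Is the blank explained by observed data in the model?** The SAP's own condition begins "Missingness depends only on observed data (e.g. prior observed HRQL scores or observed covariates". The observed variable closest to the skip rule is item 50. It is collected and scored, but it is not a model term.

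**4. How many women (assumed rates; none are in the documents).** Contributing number = 500 × share active at baseline × share of those still active × form completion.
- Low: 500 × 0.10 × 0.50 × 0.50 = 12.5, about 12 women.
- High: 500 × 0.50 × 0.80 × 0.80 = 160 women.

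**5. Can the difference be spurious (assumed mechanism)?** Simulation with 250 per arm, SD 25, baseline to follow-up correlation 0.5, no treatment effect on the score, 20% or 40% active at baseline, and 50% of baseline-active controls still active. The propensity to be active has correlation 0, 0.5 or 0.8 in size with the score, with more problems meaning less activity. The analysis is a baseline-adjusted comparison of change at one visit, to which the mixed model reduces when there is a single post-baseline visit. There were 1,500 replicates per setting, so an estimated 5% error rate has a Monte Carlo standard error of √(0.05 × 0.95 / 1500) = 0.6 percentage points.

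| Still active, other arm v control | Correlation | Mean spurious difference (points) | Type I error at nominal 5% |
|---|---|---|---|
| 50% v 50% | 0 to 0.8 | -0.05 to 0.06 | 4.1% to 5.2% |
| 60%, 69% or 79% v 50% | 0 | -0.31 to 0.01 | 3.9% to 5.5% |
| 60% v 50% | 0.5 to 0.8 | 1.1 to 2.5 | 5.4% to 9.5% |
| 69% v 50% | 0.5 to 0.8 | 2.8 to 4.9 | 8.4% to 29.7% |
| 79% v 50% | 0.5 to 0.8 | 4.2 to 7.0 | 12.1% to 52.8% |

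Both ingredients are needed. With equal activity in the arms, or with activity unrelated to the score, nothing happens. With both, the arms differ although treatment changes no woman's score.

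**The case against.** - **The scale was recognised as different.** Table 2 calls the 51-53 symptoms optional. This stands as recognition. It says nothing about how to analyse them, omits item 54, and removes neither scale from the model or from Table 14.2.20.2.
- **The descriptive reporting is largely there.** Tables 14.2.18.2, 14.2.18.4, 14.2.19.2 and 14.2.19.4 already summarise EN24 scores and single questions, raw and as change from baseline. This stands, and it makes the remedy small. The inferential table remains.
- **The model does not pretend that every woman has a value.** A reader might infer that it does. The documents do not support that: the outcome is change from baseline, so a woman whose items are blank at screening is not in the model. The difficulty is confined to women active at screening who later stop.
- **The bias is unproven.** This stands. A reader might infer that the reported difference must shrink because the worst scores drop out of the worse arm. A different assumed mechanism gives a spurious difference where there is none, and a weak link between activity and score gives almost no bias. A percentage by which the estimate is too small would also need scores for women who, under the skip rule, have none.
- **Little depends on it.** SAP 7.4 tests OS, then PFS, then ORR; quality of life is outside that sequence. This stands and sets the severity.

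**Conclusion.** The point holds for two of the 13 EN24 scales (4 of 24 items). For these, the planned arm difference is conditioned partly on a state that arises after randomisation, and a missing-at-random model is applied to values that do not exist for inactive women. The difference, interval and p-value should not be presented as a protected randomised comparison.

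That conclusion follows from the text and needs no numerical assumption. Whether bias results depends on two things the documents do not tell: whether treatment affects who stays active, and whether activity is related to the score. The simulated 1.1 to 7.0 points and the 12 to 160 contributing women only illustrate assumed rates. The simulation uses one visit, whereas the planned model would also draw on a woman's other answered visits.

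A reader might infer that the whole EN24 analysis fails or that the trial's main conclusions are touched. Neither is supported: 11 scales have no skip rule, and no primary, key secondary or safety result rests on the two that do. Severity is minor.

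**What to change.** 1. In SAP 7.2.7.2.3 and Table 14.2.20.2, exclude Sexual/vaginal problems (51-53) and Sexual Enjoyment (54) from the mixed model. Keep items 49 and 50 in it.
2. Report the two scales through the descriptive tables already planned (14.2.18.2, 14.2.18.4, 14.2.19.2, 14.2.19.4). Show the number of women to whom the items apply by arm and visit, with no between-arm p-value.
3. Report item 50 by arm and visit among all women with a form, with a cut for active stated in advance, for example any response above the lowest category.

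The cost is a sentence in the SAP and a change to table shells, with no new data. The loss is the formal comparison of two minor scales. Adding item 50 to the model instead would not serve: it would still condition on a post-randomisation state, and inactive women would still have no score.
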